9.2 Study Methods and Measurements

9.2.1 Leg Alignment

The leg alignment should be measured from an antero-posterior (A/P) view standing weight bearing full leg ('long leg') x-ray. The following axes shall be identified:

- Mechanical Axis of the femur: Axis from the center of the femoral head to the center of the distal femur.

Clinical Protocol

A Prospective, Multi-center, Study to Evaluate the Safety and Effectiveness of REAL INTELLIGENCE™ CORI™ in unicondylar knee arthroplasty (UKA) and total knee arthroplasty (TKA) procedures

Study Number: CORI.2019.07

[figure not shown]
Version: 6.0, 15/Jan/2024

Page: 49 of 122

- Mechanical Axis of the tibia: Axis from the center of the proximal to the center of the distal tibia.

The angular deviation from the neutral position (180°) shall be measured as shown as "E" in Figure 9-1. The angular deviation from the neutral position shall be recorded in the eCRF.

Figure 9-1 Leg alignment

Red: Mechanical Axis of Femur: Axis from the center of the femoral head to the center of the distal femur

Yellow: Mechanical Axis of Tibia: Axis from the center of the proximal to the center of the distal center of the tibia.

Blue: Neutral position axis (180°).

E: Deviation angle from the neutral position.

Pre-Operative Leg alignment

The pre-operative leg alignment evaluated from a standing weight bearing long leg A/P shall be recorded.

Target Leg alignment (Surgical Plan)

The operative plan for leg alignment as entered in the CORI Robotics shall be recorded in the eCRF for each subject. The planned leg alignment serves as the target for post-operative leg alignment. This may not be a neutral position.

Pre- & Post-Cementation Leg alignment

The pre-cementation leg alignment shall be recorded with the use of the CORI Robotics System (manual screenshot to be taken) with the trials implant is placed.

Once the final implant has been cemented the post-cementation leg alignment shall be recorded with the CORI Robotics System (manual screenshot to be taken).

Clinical Protocol

A Prospective, Multi-center, Study to Evaluate the Safety and Effectiveness of REAL INTELLIGENCE™ CORI™ in unicondylar knee arthroplasty (UKA) and total knee arthroplasty (TKA) procedures

Study Number: CORI.2019.07

Version: 6.0, 15/Jan/2024

Page: 50 of 122

Post-Operative Leg alignment

The leg alignment shall be assessed post-operatively and 6 weeks after surgery on standing weight bearing long leg A/P X-ray and lateral X-ray. Optionally, leg alignment can be assessed optionally at 12 months, in case a standing weight bearing long leg A/P X-ray is taken at 12 months.

Post-operative leg alignment is achieved when the deviation from the subject specific target does not exceed ± 3 degrees.

All leg alignment measures will be added to the eCRF.

9.2.2 Component Alignment

Component alignment will be assessed on long leg standing A/P X-rays and standard non weight bearing lateral X-rays taken 6 weeks after surgery (or at discharge). The following angles will be evaluated on the X-rays and recorded in the eCRF:

A/P View

Femoral A/P Angle: From the A/P radiograph, the femoral flexion angle is to be obtained using standard radiographic tools. Femoral flexion angle is defined as the angle formed between a line across the base of the femoral condyles and a line that is centered along the femoral canal

Tibial A/P Angle: From the A/P radiograph, the tibial angle denotes the angle formed on the medial side of the knee from intersecting lines parallel to the tibial base plate and a line drawn parallel to the tibial canal (Figure 9-2).

Total Valgus Angle: Is the sum of the femoral flexion angle and the tibial angle.

Figure 9-2 A/P View

A: Femoral A/P Angle

B: Tibial A/P Angle

A+B: Total Valgus Angle

Clinical Protocol

A Prospective, Multi-center, Study to Evaluate the Safety and Effectiveness of REAL INTELLIGENCE™ CORI™ in unicondylar knee arthroplasty (UKA) and total knee arthroplasty (TKA) procedures

Study Number: CORI.2019.07

Version: 6.0, 15/Jan/2024

[figure not shown]
Page: 51 of 122

Lateral View

Femoral Flexion Angle: The lateral view femoral flexion angle is obtained from the intersection of a line from the center of the femoral implant to the top of the femur with a line through the femoral canal. The angle is measured on the proximal side of the intersection.

Tibial Lateral Angle: The lateral view tibial angle is the angle obtained from the intersection of a line drawn parallel to the bottom of the tibial base insert and a line through the center of the tibial base and the tibial canal (Figure 9-3).

Figure 9-3 Lateral View

X: Femoral Flexion Angle

Y: Tibial Lateral Angle

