 - Treatment of fractures that are unmanageable using other techniques.
- Unicompartmental knee implants are single use only and are intended for implantation only with bone cement. HA coated unicompartmental knee implants are available outside the US for use without bone cement.

Clinical Protocol

A Prospective, Multi-center, Study to Evaluate the Safety and Effectiveness of REAL INTELLIGENCE™ CORI™ in unicondylar knee arthroplasty (UKA) and total knee arthroplasty (TKA) procedures

Study Number: CORI.2019.07

Version: 6.0, 15/Jan/2024

Page: 28 of 122

ZUK Unicompartmental Knee

The ZUK system is designed for the surface reconstruction of individual femoral/tibial condyles. Use of this device does not preclude subsequent reconstructive surgery with a stabilizing type device or a total knee replacement.

Indications for Use of the ZUK Unicompartmental Knee are listed below:

- This device is indicated for patients with:
- Painful and/or disabling knee joints due to osteoarthritis or traumatic arthritis.
- Previous tibial condyle or plateau fractures with loss of anatomy or function
- Varus or valgus deformities.
- Revision of previous arthroplasty procedures.
- This device is indicated for cemented use only.
- The ZUK Unicompartmental Knee System is designed for use when load bearing ROM is expected to be less than or equal to 155 degrees.

STRIDE Unicondylar Knee System

The STRIDE Unicondylar Knee System is a unicompartmental prosthetic implant that resurfaces one femoral condyle and one side of the tibial plateau. The femoral component is made of cobalt chrome and the tibial component is composed of a titanium tibial tray with a ultra-high molecular weight polyethylene insert that snaps into place. The device is non-constrained; the articulating surface of the Intra-high molecular weight polyethylene insert is flat and joint stability is maintained by ligaments and other soft tissue surrounding the knee.

The STRIDE Unicondylar Knee Systems are indicated for patients with:

- Painful and/or disabling knee joints due to osteoarthritis or traumatic arthritis.
- Previous tibial condyle or plateau fractures with loss of anatomy or function.
- Varus or valgus deformities.
- Revision of previous arthroplasty procedures.
- These devices are indicated for cemented use only.

Smith+Nephew Total Knee Replacement Systems: JOURNEY II Knee Systems, LEGION Hinge Knee System, and GENESIS II Total Knee System

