8.3.2 Secondary Endpoints

The following secondary endpoints have been defined for this study in order to evaluate the safety and performance of the CORI Robotics:

- Component Alignment 6 weeks post-surgery
- Radiographic assessment (Presence of radiolucent lines, osteolysis & implant migration) 12 months post-surgery
- 2011 Knee Society Score (KSS) at baseline, 6 weeks, 6 and 12 month post-surgery
- Oxford Knee Score (OKS) at baseline, 6 weeks, 6 and 12 month post-surgery
- Forgotten Joint Score (FJS) at 6 weeks, 6 and 12 month post-surgery

Clinical Protocol

A Prospective, Multi-center, Study to Evaluate the Safety and Effectiveness of REAL INTELLIGENCE™ CORI™ in unicondylar knee arthroplasty (UKA) and total knee arthroplasty (TKA) procedures

Study Number: CORI.2019.07

Version: 6.0, 15/Jan/2024

Page: 41 of 122

- Five-level EuroQol five-dimensional (EQ-5D-5L) VAS & index scores at baseline, 6 weeks, 6 and 12 month post-surgery

Secondary endpoints are aligned to the secondary study objectives of generating safety and performance evidence related to the use of the CORI surgical system. Assessing alignment, radiographic image assessment and patient-reported outcome measures (PROMS) are key variables in determining the success of UKA and TKA procedures. These endpoints have been previously evaluated with the predicate NAVIO surgical system and ongoing assessment of these secondary endpoints under this study will support safety and efficacy of these procedures performed with the CORI surgical system.

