10.4.2 Analysis of Secondary Endpoint

All analyses on the secondary endpoints will be carried out separately in the CORI Robotics UKA and CORI Robotics TKA groups.

Component Alignment

Femoral components (internal rotation, valgus and anterior tilt) and tibial components (internal rotation, valgus, and posterior slope) will be summarized using descriptive summary characteristics for continuous variables.

Clinical Protocol

A Prospective, Multi-center, Study to Evaluate the Safety and Effectiveness of REAL INTELLIGENCE™ CORI™ in unicondylar knee arthroplasty (UKA) and total knee arthroplasty (TKA) procedures

Study Number: CORI.2019.07

Version: 6.0, 15/Jan/2024

Page: 57 of 122

Standard Radiographic Assessment

Radiolucent lines (mm) by zone and visit will be summarized using descriptive statistics for continuous variables.

2011 Knee Society Score (KSS)

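### In the UKA group, the femoral A/P angle and the Total Valgus Angle built on it do not measure the coronal alignment of the femoral component

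*Combined protocol and SAP*

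**What the plan says.** Section 8.3.2 lists "Component Alignment 6 weeks post-surgery" as a secondary endpoint. Section 9.2.2 defines four measured angles and one sum, with the same wording for UKA and TKA.

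- **Femoral A/P angle.** "Femoral flexion angle is defined as the angle formed between a line across the base of the femoral condyles" and a line centred along the femoral canal. No implant surface is named.
- **Tibial A/P angle.** Formed medially from "intersecting lines parallel to the tibial base plate and a line drawn parallel to the tibial canal".
- **Total Valgus Angle.** "Is the sum of the femoral flexion angle and the tibial angle".
- **Lateral femoral flexion angle.** Uses "a line from the center of the femoral implant to the top of the femur", against the femoral canal.
- **Lateral tibial angle.** Uses the underside of the tibial base insert, against a line through the tibial base and canal.

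Section 6.1.1 describes one of the UKA systems, STRIDE, as "a unicompartmental prosthetic implant that resurfaces one femoral condyle and one side of the tibial plateau". It says of the Journey unicompartmental implants that they restore either compartment of the knee.

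Section 10.4.2 analyses secondary endpoints separately by group. For component alignment it plans descriptive summaries of "Femoral components (internal rotation, valgus and anterior tilt) and tibial components", with a matching list for the tibia.

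**The concern.** A measure of component alignment should change when the component's orientation changes, and should stay still when it does not. The femoral A/P angle meets this in a TKA, where the condylar surface is the implant. A UKA replaces one condyle, so the other end of the line sits on the patient's own bone. The reading then depends on how far distally the component sits relative to the native condyle, and on the native anatomy, rather than on the component's varus or valgus orientation alone.

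This matters because the UKA group is summarised on its own, because section 8.3.2 counts alignment among the key variables for the success of both procedures, and because section 4.1 links UKA revision to malposition or malalignment. Section 9.2.2 defines no other coronal femoral angle. Followed as written, the UKA data could not support a statement about the coronal orientation of the femoral component.

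**Working it through.** The plan states no figure to reproduce here. The check classifies each reference line, then asks what the condylar line responds to.

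**Step 1. What each quantity refers to in a UKA (section 9.2.2)**

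| Quantity | Reference line | Tied to the implant in a UKA? |
|---|---|---|
| Femoral A/P angle | Base of the femoral condyles | No: one implanted, one native condyle |
| Tibial A/P angle | Tibial base plate | Yes |
| Total Valgus Angle | Femoral A/P plus tibial A/P | No: inherits the femoral term |
| Lateral femoral angle | Femoral implant | Yes |
| Lateral tibial angle | Tibial base insert and base | Yes |

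The text uses the name femoral flexion angle for both the A/P and the lateral femoral measure. The key to Figure 9-2 settles which one enters the sum: Total Valgus Angle is A+B, and A is the femoral A/P angle. So 2 of 5 quantities are affected, in 40 of 80 subjects.

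**Step 2. What moves the condylar line**

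Let w be the mediolateral distance between the two condylar low points, and d the change in distal height of the replaced condyle. Starting from a level line, the rotation is

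change in angle = atan(d / w).

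The documents do not give w. I assume 40 to 55 mm.

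| d | w = 40 mm | w = 55 mm |
|---|---|---|
| 1 mm | atan(1/40) = 1.43° | atan(1/55) = 1.04° |
| 2 mm | atan(2/40) = 2.86° | atan(2/55) = 2.08° |

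These shifts need no change in the component's tilt. Conversely, if the component tilts about its own low point, that point stays where it is, so d = 0 and the change is atan(0) = 0°. Tilt about any other point, such as a fixation peg, registers only through the height change it causes at the low point.

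**Step 3. Does the protocol treat these as one quantity?**

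No. Section 4.2.3, on UKA studies of the predicate system, lists the coronal femoral angle and joint line deviation as separate parameters. The 9.2.2 definition merges them in a UKA.

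**The case against.** Several points on the other side stand.

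- **Most of the endpoint is sound.** A reader might infer that component alignment as a whole fails to measure the implant in UKA. The documents do not support that: three of the four measured angles name implant parts.
- **The figure is missing.** The text says the condyles, in the plural, but does not say both, and Figure 9-2 is not shown. The figure might place the line differently. Even so, the written rule is common to both groups and offers no UKA line.
- **The link to 10.4.2 is an inference.** It is tempting to say that 10.4.2 reports this angle as femoral component valgus. That section names neither the femoral A/P angle nor the Total Valgus Angle. It also lists internal rotation, for which 9.2.2 has no angle; that is a separate mismatch affecting both groups.
- **No component would be misclassified.** A reader might expect good components to be called abnormal, or the reverse. The protocol sets no target or limit for any component angle, and the analysis is descriptive.
- **The angle is not blind to placement.** Distal height is part of component position. The fault is that height and tilt cannot be separated, and the zero response holds only for tilt about the low point.

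None of this makes the femoral A/P angle, as written, a measure of coronal component orientation in a UKA.

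**Conclusion.** The point holds for two quantities in one group. As defined in 9.2.2, the femoral A/P angle and the Total Valgus Angle in the 40 UKA subjects mix component height, component tilt and native anatomy, and do not isolate the coronal alignment of the femoral component. About 1.0 to 1.4 degrees per millimetre of distal height is the size of the confounding.

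This rests on the plain reading of the plural condyles, on the assumed spacing of 40 to 55 mm, and on the geometry of a line that starts level. The consequence is limited. The endpoint is secondary and descriptive, the primary endpoint in 9.2.1 uses the mechanical axes, and the sample size plays no part. It is worth correcting because the rule yields a quantity other than the one intended in half of the study, and the correction is cheap.

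**What to change.** 1. In 9.2.2, keep the present femoral A/P definition for TKA.
2. For UKA, define the femoral A/P angle from one named reference line on the femoral component itself, against the femoral canal line already in use. The sponsor should choose a single line that can be read on the A/P film for every UKA system in Table 6-1. The defect is in the distal line only, so the proximal reference need not change.
3. Report Total Valgus Angle for TKA only.
4. In 10.4.2, state which 9.2.2 angle supplies femoral valgus in each group, and carry this into the SAP, which section 10 says will be finalised before database lock.

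The cost is wording in the protocol and the eCRF guideline, plus one angle re-measured on UKA films already read. Section 9.1.4 already requires the 6-week long-leg film, so no new image is needed. The UKA and TKA femoral A/P angles would no longer be the same measure, but they are already summarised separately.

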9.2.3 Standard Radiographic Evaluation

Standard radiographic evaluation on antero-posterior (A/P) and lateral (L) views shall be performed 12 months after surgery in order to identify any radiographic observations such as radiolucent lines around the implant components. The presence of radiolucent lines, osteolysis & implant migration shall be recorded in the eCRF.

9.2.4 2011 Knee Society Score (KSS)

The 2011 Knee Society Score will be collected at the pre-operative visit and 6 weeks, 6- and 12-months after surgery.

The 2011 KSS is a validated tool that combines an objective physician-derived component with a subjective subject-derived component [46, 47]. The KSS consists of 36 questions and provides sub-scores across 4 dimensions as shown in Table 9-2.

Clinical Protocol

A Prospective, Multi-center, Study to Evaluate the Safety and Effectiveness of REAL INTELLIGENCE™ CORI™ in unicondylar knee arthroplasty (UKA) and total knee arthroplasty (TKA) procedures

Study Number: CORI.2019.07

Version: 6.0, 15/Jan/2024

Page: 52 of 122

Table 9-2 Knee Society Score 2011

#	Sub-Score	# Questions	Range	Completion by
1	Objective Knee Score	7	0-100	Surgeon
2	Subject Satisfaction Score	5	0-40	Subject
3	Subject Expectation	3	3-15	Subject
4	Functional Knee Score	19	0-100	Subject

The Objective Knee Score is rated by the clinician and assesses a range of clinical outcomes: UKA/TKA alignment, stability, ROM and symptoms. The Subject Satisfaction Score assesses the satisfaction with 5 daily activities (sitting, lying in bed, getting out of bed, light household duties, and leisure activities). The Subject Expectation Score evaluates the subject's expectations prior to surgery. The post-operative questions differ from the pre-operative questions and ask if the subject's pre-operative expectations have been met. As the pre- and post-operative scores are based on different questions, they cannot be directly compared. The Functional Knee Score is derived from assessments of walking and standing, standard activities, advanced activities, and discretionary activities.

A paper questionnaire will be provided by the Sponsor to be completed by the subject. Responses for the KSS will then be recorded in the eCRF.

9.2.5 Oxford Knee Score (OKS)

The Oxford Knee Score (OKS) will be collected at the pre-operative visit and 6 weeks, 6- and 12-months after surgery.

The Oxford Knee Score (OKS) is a Patient Reported Outcome questionnaire that was developed to specifically assess the patient's perspective of outcome following Total Knee Arthroplasty. The OKS is a patient self-completion PRO containing 12 equally weighted questions on activities of daily living. The OKS has been developed and validated specifically to assess perceived function and pain answered on a Likert scale after TKA [48, 49]. Responses to each question ranges from 0-4 with a range of a possible overall score from 0-48. A score of 0 is the worst possible outcome while a score of 48 is the best possible outcome. The benefit to this questionnaire is that it is short, practical, reliable, valid and sensitive to clinically important changes over time.

A paper questionnaire will be provided by the Sponsor to be completed by the subject. Responses for the OKS will then be recorded in the eCRF.

Clinical Protocol

A Prospective, Multi-center, Study to Evaluate the Safety and Effectiveness of REAL INTELLIGENCE™ CORI™ in unicondylar knee arthroplasty (UKA) and total knee arthroplasty (TKA) procedures

Study Number: CORI.2019.07

Version: 6.0, 15/Jan/2024

Page: 53 of 122

9.2.6 Forgotten Joint Score (FJS)

The Forgotten Joint Score (FJS) will be collected at 6 weeks, 6- and 12-months after surgery. A paper questionnaire will be provided by the Sponsor to be completed by the subject.

The FJS comprises measures for the assessment of joint-specific patient reported outcomes. This questionnaire focuses on the study subject's awareness of the partially or fully replaced knee joint in everyday life. Joint awareness can be simply defined as any unintended perception of a joint [50]. Subjects are asked to rate their awareness of their knee arthroplasty in 12 questions with a five point Likert response format: "Never", "almost never", "seldom", "sometimes" and "mostly". The item scores are summed and linearly transformed in a 0 to 100 scale with a high value reflecting the ability of the subject to forget about the replaced knee joint during the activities of daily living.

A paper questionnaire will be provided by the Sponsor to be completed by the subject. Responses for the FJS will then be recorded in the eCRF.

9.2.7 Robotic System Time & Cutting Time

The CORI Robotic System Time and the Cutting Time of the robotic drill shall be collected post-operatively.

The CORI Robotics Case Report, including case logs, will be extracted from the CORI system via USB and time data will be extracted for CORI Robotic System Time and the Cutting Time

In the case logs, the following time stamps will be recorded in the log file of the CORI Robotics Case Report:

1. State-Machine transition : [Adjust Camera] --> [Checkpoint Definition]
2. State-Machine transition : [Checkpoint Verification] --> [Remove Bone]
3. State-Machine transition : [Remove Bone] --> [Baseline Stress ROM Collection]

Robotics System Time

Robotics System starts with the checkpoint definition until the bone is removed. This is calculated by the time difference between #3 and #1.

Clinical Protocol

A Prospective, Multi-center, Study to Evaluate the Safety and Effectiveness of REAL INTELLIGENCE™ CORI™ in unicondylar knee arthroplasty (UKA) and total knee arthroplasty (TKA) procedures

Study Number: CORI.2019.07

Version: 6.0, 15/Jan/2024

Page: 54 of 122

Cutting Time

The Cutting Time of the robotic drill is the time from the start until the end of bone removal and is calculated by the time difference between #3 and #2.

The Robotics System time and the cutting time of the robotic drill will not be recorded in the eCRF as they will be extracted directly from the CORI Robotics Case Report.

9.3 Health Economics/Quality of Life

The EQ-5D-5L questionnaire will be collected at the pre-operative visit as well as 6 weeks, 6- and 12-months after surgery. A paper questionnaire will be provided by the Sponsor to be completed by the subject.

The EQ-5D-5L essentially consists of 2 pages: the EQ-5D descriptive system and the EQ visual analogue scale (EQ VAS).

The descriptive system is used to describe the subject's health state and consists of five dimensions: mobility, self-care, usual activities, pain/discomfort, and anxiety/depression. Each dimension has 5 levels to choose the most appropriate answer: no problems, slight problems, moderate problems, severe problems, and extreme problems. The subject is asked to indicate his/her health state by marking the most appropriate statement in each of the five areas [51].

The EQ VAS records the subject's self-rated health on a vertical visual analogue scale. The endpoints on the scale are labelled "The best health you can imagine" and "The worst health you can imagine". The VAS can be used as a quantitative measure of health outcome as judged by the individual respondents.

A paper questionnaire will be provided by the Sponsor to be completed by the subject. Responses for the EQ-5D-5L Score will then be recorded in the eCRF.

